### Primary Analysis for FDA

The null and alternative hypotheses for the primary endpoint are defined below

$$H_0: \mu_{\text{best-GS010}} = \mu_{\text{best-Sham}}$$

$$H_1: \mu_{\text{best-GS010}} \neq \mu_{\text{best-Sham}}$$

Where  $\mu$  presents the mean change from baseline to Week 48 in LogMAR and “best” indicates best-seeing eyes.

The primary analysis will be performed on the ITT population. The change from baseline to Week 48 in the LogMAR acuity will be the primary response. The change from baseline of the best-GS010 eyes will be compared to the change from baseline of the best-Sham eyes (inter-subject comparison) using analysis of covariance (ANCOVA) including treatment as a main effect

- and baseline LogMAR

as a covariate in the model. The analysis will be performed based on alpha of 0.05. The statistical significance in favor of Best-GS010 eyes against Best-sham eyes will show evidence of the advantage of using GS010 in the best eye for halting visual acuity loss or improving visual acuity in subjects with LHON with a duration of vision loss of more than 6 months and up to 12 months. The difference in the mean change from baseline (adjusted mean difference) to Week 48 between the two treatment groups and associated 95% confidence interval will be reported.

The center will not be included in the analysis as the number of subjects recruited per site will be very small. However, stratification by geographical area will be performed as a sensitivity analysis. Neighboring regions will be pooled together to reach at least 9 subjects per geographical entity. The pooling will be performed during the masked review of data. An additional model will add the treatment by geographical area interaction to test for lack of generalizability of treatment effect.

The same analysis will be repeated for worst-GS010 eyes against worst-Sham eyes.

All the model diagnostics will be checked.

#### Secondary analysis of primary end point for FDA

Secondary Analysis of primary variable for FDA will be based on the methodology described above for primary analysis of primary variable for EMA. For secondary analysis, change of LogMAR from baseline at Week 48 will be compared between all-GS010 eyes and all-Sham eyes (intra-subject comparison). The difference in the mean change from baseline to Week 48 between the two treatment groups and associated 95% confidence interval will be reported.

#### Other Analysis

LogMAR and ETDRS score for each visit and change from baseline will be summarized by treatment group (Best-GS010/Best-Sham). LogMAR and ETDRS score for each visit and change from baseline will also be summarized by treatment group (Worst-GS010/Worst-Sham).

A graph presenting the mean of each treatment group at baseline and the mean at Week 48 will be presented. The graph will be useful to assess whether the difference in the change from baseline is mainly due to the difference at baseline or the difference at Week 48.

#### Sensitivity Analysis

Primary analysis with the same model will be repeated for the following lists.

- 1) Per protocol
- 2) Randomized subjects including those not treated
- 3) Secondary handing of missing data
- 4) Model with country effect
- 5) Model excluding major outliers if any (defined as a standardized endpoint greater than the absolute value of 4.0)
- 6) Analysis of absolute Week 48 LogMAR values, without covariate adjustment
- 7) Baseline GCL layer thickness/volume and topographical map
- 8) Duration of vision loss at the time of treatment as a covariate

All these analyses will be presented in a forest plot displaying treatment effect, 95% confidence intervals and p-value.

10) Non-parametric Analysis: Wilcoxon Rank-Sum test will be performed as a sensitivity analysis to compare between Best-GS010 eyes and Best-Sham eyes.

## **9.5.2 Methods for Handling Dropouts and Missing Data**

Method for dealing with missing data has been detailed in [Section 5.5.1](#)

## **9.5.3 Multiplicity**

All the type I error (alpha=0.05) will be spent for the primary end point analysis. All the other analysis will be supportive analysis of the primary end point. Therefore, no adjustment of multiplicity will be necessary.

## **9.5.4 Pooling of Sites**

No pooling of sites will be applied for the primary analysis. However, a stratification by geographical area will be performed as a sensitivity analysis. Neighboring countries can be pooled together to reach at least 9 subjects per geographical entity. The pooling will be performed during the masked review of data.

## **9.5.5 Secondary Variables**

### GCL thickness/volume and topographical map

The change of RGC layer thickness/volume and topographical map from baseline to week 48 will be based on ANCOVA including the subject and the eyes of the subject as random factors, the treatment, and the baseline GCL thickness/volume as covariates in the model. The analysis will be performed based on alpha of 0.05. The difference in the mean change from baseline (adjusted mean difference) to Week 48 between the two treatment groups (all-GS010 vs all-Sham and best-GS010 vs best-Sham) and associated 95% confidence interval will be reported.

### RNFL temporal quadrant and papillo macular bundle

The change of RNFL temporal quadrant and papillo macular bundle from baseline to week 48 will be analyzed same way as GCL volume and topographical map.

### Change from baseline of the LogMAR scores at Week 96

The treatment estimate at Week 96 will be based on the same statistical approach as the primary endpoint analysis for EMA between all-GS010 and all-Sham and Best-GS010 vs Best-Sham.

### Time course of the response

Time course analysis will compare time course of the response up to Week 48 using the mixed model procedure. The change from baseline to Week 48 in the LogMAR will be the response. The change from baseline of all GS010 eyes will be compared to the change from baseline of all sham eyes using a mixed model of repeated measure (MMRM) including the subject and the eyes of the subject as random factors, the treatment, Visit, eye status at baseline (Best or worst), interaction between eye status at baseline and treatment, interaction between visit and treatment and baseline as covariates in the model. The estimate of treatment effect at various time points and its 95%CI (without adjustment for multiplicity) will be presented. Unstructured covariance structure will be fitted. In case of any convergence problem with this covariance structure other covariance structures will be used.

Three graphical presentations will be performed:

- 1) A graph with the time course of the response for the treated best eye, the sham best eye, the treated worst eye and the untreated worst eye.
- 2) A graph with the time course of the response of the treated eye (irrespective of the status at baseline) and the sham eye (irrespective of the response).
- 3) A graph with the time course of the response of the treatment effect (delta between treatment groups) for the best Seeing Eye at baseline and for the worst Seeing Eye at baseline.

In the graphs the pertinent p values including that of interaction between eye status and treatment, time effect, treatment effect, treatment by time interaction will be displayed.

Two additional analyses with the same model (excluding eye status and treatment interaction) for the best-seeing Eye and for the worst-seeing will be performed (sub-group analysis).

The same analysis will be continued for up to Week 96-time course.

All the model diagnostics will be investigated.

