## Secondary Objectives:

- To assess the effect of GS010 on parameters measured with high resolution spectral-domain optical coherence tomography (SD-OCT), including Retinal Ganglion Cell (RGC) layer, inner and outer nuclear layer (INL and ONL) thickness/volume, Retinal Nerve Fiber Layer (RNFL) thickness and topographical map analysis of these anatatomical regions.

- To evaluate the efficacy of GS010 compared with sham on the visual acuity (LogMAR) in a dynamic perspective through the comparison of the time course of the response.
- To verify whether the efficacy at Week 48 and at Week 96 of GS010 compared with sham and measured by the change from baseline of the LogMAR is dependent upon the treatment of the best- or worst-seeing-eye.
- To verify whether the rate of responders at Week 48 and 96 is dependent upon the treatment received and whether the magnitude of the treatment effect is dependent upon the treatment of the best- or worst-seeing eye at entry.
- To assess the effect of GS010 on standardized automated visual fields obtained with the Humphrey Visual Field (HVF) Analyzer II.
- To assess the effect of GS010 on contrast sensitivity measured with the Pelli-Robson chart.
- To assess the effect of GS010 on color vision measured with the Farnsworth-Munsell 100 Hue color test.

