### 3. STUDY DESIGN

#### 3.1 OVERALL DESIGN

[figure not shown]
GS-LHON-CLIN-03B is a Phase III double-masked, sham-controlled, multicenter, multi-country study. Recruitment is competitive.

Both eyes will receive standard antiseptic preparation, administration of topical local ocular anesthetic agents and will undergo pupillary dilation. Administration of an intra-ocular pressure lowering agent will precede treatment. GS010 will be administered once during the study via a single intravitreal (IVT) injection. Sham IVT injection will be performed by applying pressure to the eye at the location of a typical procedure using the blunt end of a syringe without a needle.

The right eye of each subject will be randomly allocated to receive either GS010 or sham treatment in a 1:1 allocation ratio. The fellow (left) eye will receive the treatment not allocated to

the right eye. Therefore, each subject will receive GS010 in one eye and sham treatment in the fellow eye.

The schematic design of the study design is given below:

An algorithm with a testing hierarchy will be employed to determine the best- and worst-seeing eye of each subject prior to randomization. The randomization will be based on the right and left eye, because if the right eye is treated the left eye will receive sham and vice versa the treatment groups will be automatically balanced. However, the best- or worst-seeing eye at entry can be a confounding factor, and it cannot be discarded that the treatment effect will be the same in the best and worst seeing-eye. Secondarily, in order to verify this hypothesis with optimal power, an adaptive randomization technique called Efron's minimization ([Efron 1971](#)) method will be used to minimize the imbalance of treatment groups between the best-seeing eyes and worst-seeing eyes.

Masking will be accomplished with sham injection of the fellow eye. Thus treatment allocation will be double-masked for both the subject and the investigation (follow-up) team, except the physician and medical team that will perform the GS010 administration and sham injection and the first follow-up visit. Centralized analysis of the Early Treatment Diabetic Retinopathy Study (ETDRS) visual acuity results, automated visual fields, SD-OCT, color vision and contrast sensitivity will be performed.

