### 4.3 PREDETERMINED COVARIATES AND PROGNOSTIC FACTORS

RGC layer, INL, ONL thickness/volume and topographical maps of these anatomical regions, best or worst-seeing eye (eye status) as determined prior to randomization and duration of vision loss at the time of treatment could be significant prognostic factors for the treatment effect. Sensitivity analysis will be performed for RGC layer thickness/volume and topographical map and eye status (best or worst-seeing eye) and duration of vision loss at the time of treatment by including them in the primary model as a covariate.

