### Sensitivity Analyses

The primary analysis with the same model will be repeated for the following lists.

- 1) Per protocol
- 2) Randomized subjects even if they were not treated and assigned treatment by randomization instead of actual treatment received
- 3) Secondary handling of missing data
- 4) Model with geographical area effect
- 5) Model excluding major outliers if any
- 6) Analysis of absolute Week 48 LogMAR values
- 7) Baseline GCL thickness/volume and topographical map
- 8) Best or worst-seeing eye (eye status) added as a binary covariate
- 9) Duration of vision loss at the time of treatment added as a covariate in the model

All these analyses will be presented in a forest plot displaying treatment effect, 95% confidence intervals and p-value. The analysis will also be presented in tabular format.

- 10) Non-parametric Analysis: Wilcoxon signed-rank test will be performed as a sensitivity analysis to compare between all-GS010 eyes and all-Sham eyes

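### The SAP keeps its best/worst-eye objectives at Weeks 48 and 96, but tests the difference in LogMAR effect only as one term common to all visits and does not test it for responders

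*SAP*

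**What the plan says.** **Objectives.** SAP section 2 asks whether LogMAR efficacy at Weeks 48 and 96 "is dependent upon the treatment of the best- or worst-seeing-eye". For responders at the same weeks it asks "whether the magnitude of the treatment effect is dependent upon the treatment of the best- or worst-seeing eye at entry". SAP 3.1 explains the minimisation as a design choice made "in order to verify this hypothesis with optimal power, an adaptive randomization technique".

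**Protocol tests.** Protocol 12.4.1 fits a Week 48 LogMAR model with random subject, treatment, eye status and their interaction, and flags an interaction at P<0.15. Protocol 12.4.2 adds a homogeneity test of the responder effect between subjects whose better eye and subjects whose worse eye was treated.

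**SAP analyses that involve eye status.**
- The time-course model (SAP 9.5.5) includes "interaction between eye status at baseline and treatment, interaction between visit and treatment". Its result is planned as a display: "In the graphs the pertinent p values including that of interaction between eye status and treatment".
- The same section plans separate best-eye and worst-eye models and a graph of the treatment effect over time by eye status.
- SAP 9.5.1 plans best-eye and worst-eye ANCOVAs at Week 48.
- SAP 4.3 says that eye status and other factors "could be significant prognostic factors for the treatment effect". The matching sensitivity analysis is "Best or worst-seeing eye (eye status) added as a binary covariate".
- The subject-responder and eye-responder tests in SAP 9.5.5 do not mention eye status.

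**The concern.** Whether the effect depends on eye status is a question about a difference between two treatment effects at a stated week. The SAP keeps the question but not the protocol's tests of it.

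The remaining interaction term assumes that the best/worst difference is the same at every visit from Week 2 on. A difference that develops late would be diluted. Eye status as a covariate adjusts the mean and cannot show that the treatment effect differs. Separate best-eye and worst-eye results invite the reader to compare one p-value with another, which is not a test of their difference.

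At stake are two stated secondary objectives and one later decision: the meta-analysis in Protocol 12.4.1 chooses its model by whether the effect depends on eye status.

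**Working it through.** **1. Plan's own figure.** SAP 3.3 gives SD 0.594 for the between-eye difference in change, a target of 0.3 LogMAR, 36 subjects and 84% power. The noncentrality is 0.3/0.594 × √36 = 3.03. With 35 df and two-sided alpha 0.05, power is 83.8%, so the figure reproduces and the SD can be used below.

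**2. What the time-course term targets.** The efficacy visits to Week 48 are Weeks 2, 4, 8, 12, 24 and 48 (the 24-hour visit is safety only, Protocol 7.3.1). The model has no eye-status-by-treatment-by-visit term. With visit covariance V, the common interaction estimates w'δ, where w = V⁻¹1/(1'V⁻¹1) and δ is the true difference at each visit. Let δ grow linearly to 0.3 at the last visit. Assumed correlations: compound symmetry 0.5 and 0.8; AR(1) by visit 0.5, 0.7 and 0.9; exponential 0.8 and 0.9 per 12 weeks.

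| Period | Equal SD | SD doubling from Week 2 to last visit |
|---|---|---|
| To Week 48 (6 visits) | 0.10 to 0.16 | -0.11 to 0.06 |
| To Week 96 (8 visits) | 0.10 to 0.15 | -0.15 to 0.06 |

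With equal weights the Week 48 value is 0.3 × (2+4+8+12+24+48)/(6×48) = 0.3 × 0.340 = 0.10. Negative targets arise because late, more variable and highly correlated visits can receive negative weights; the term is not a simple average.

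**3. A Week 48 test.** Each subject contributes both eyes. The best-eye effect minus the worst-eye effect equals the difference in mean two-eye sum between best-eye-treated and worst-eye-treated subjects. If r is the between-eye correlation, SD(sum) = 0.594 × √((1+r)/(1-r)) and SE = SD(sum) × √(2/18), assuming an 18/18 split. Power is for a 0.3 difference, 34 df; the CI half-width is 2.032 × SE.

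| r (assumed) | SE | Power at P<0.15 | 95% CI half-width |
|---|---|---|---|
| 0 | 0.198 | 52% | 0.40 |
| 0.5 | 0.343 | 29% | 0.70 |
| 0.8 | 0.594 | 20% | 1.21 |

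For the linear profile with equal variances, the time-course term has 21–32% power at r = 0 and 17–21% at r = 0.5. If the difference is a constant 0.3, it has 58–84% and 32–49%.

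**4. Responders.** Write b and w for the best- and worst-eye response rates, T for GS010 and S for sham. If the best eye is treated, the within-subject effect is bT - wS; if the worst eye is treated, it is wT - bS. The difference between the two is

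(bT - wS) - (wT - bS) = [(bT - bS) - (wT - wS)] + 2(bS - wS).

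An unadjusted comparison of paired effects therefore carries twice the sham best-minus-worst difference. The count of responding eyes does not:

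(bT + wS) - (bS + wT) = (bT - bS) - (wT - wS).

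Take no treatment effect and assumed sham rates of 20% (best) and 10% (worst). The paired comparison then has expected value 2 × 0.10 = 0.20. In simulation (18/18, between-eye correlation 0.3 to 0.8) a Wald test of it was significant at 0.15 in 48–64% of trials, or 44–60% with n-1 variances. At 30%/15% it was 63–81%. Comparing responding eyes per subject gave 15%, with a 95% CI half-width of 0.36–0.48 and 38–54% power at P<0.15 for a 0.30 difference in effect.

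**The case against.** **Both eye effects are already estimated.** This stands. SAP 9.5.1 gives best-eye and worst-eye effects at Week 48, and the subgroup time-course models and the third graph extend this to Week 96. A reader might infer that the SAP ignores eye status; it does not. What is missing is a test and interval for the difference at each week.

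**The SAP has responder tests.** It does: a randomization test for subject responders and McNemar for eye responders. A reader might infer that responders go untested, but only the comparison by eye status is absent.

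**The 0.15 rule no longer decides anything here.** Largely right. In the protocol it determined whether the by-eye ANCOVAs were run. The SAP runs them unconditionally, and best-versus-best is the FDA primary. The rule's remaining use is the meta-analysis model choice, and the protocol does not say which study's test decides that.

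**The common term can be the better test.** True if the difference is constant over visits. If the SD also doubles, its power for a constant 0.3 is at least 94% at r = 0 and 62–81% at r = 0.5. That is a reason to keep it, but it does not answer a question about Week 48 or Week 96.

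**Dropping the protocol's responder test may have been sensible.** Possibly. Protocol 12.4.2 cites a method without giving its statistic, so whether that method avoids the sham best/worst difference cannot be checked from the documents. The false-signal rates above belong to an unadjusted Wald comparison with assumed sham rates, not to the cited method. The gap is that nothing replaced it.

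**Everything beyond the primary is supportive (SAP 9.5.3).** True. It limits the consequence, but the objectives remain stated.

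**Conclusion.** The gap is real and limited to secondary objectives. For LogMAR, the SAP's only interaction test addresses one difference common to all visits. Under the assumed covariances, a 0.3 LogMAR difference growing linearly to Week 48 is targeted as 0.10 to 0.16 with equal variances and as -0.11 to 0.06 if the SD doubles. These are illustrations, not bounds; a constant difference is targeted correctly. For responders, no comparison by eye status is planned at either week.

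Neither primary analysis is affected. A reader might also infer that restoring the tests would settle the question. It would not: the Week 48 test has 52%, 29% or 20% power at assumed between-eye correlations of 0, 0.5 or 0.8. The correlations, the time profiles, the 18/18 split and the sham response rates are assumptions; the SD of 0.594 is the SAP's.

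**What to change.** Amend the SAP before the code is broken, because Protocol Appendix V allows no amendment afterwards.

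- **LogMAR:** add the interaction model of Protocol 12.4.1 at Weeks 48 and 96. Equivalently, add eye-status-by-visit and eye-status-by-treatment-by-visit terms to the time-course model, with contrasts at those weeks. Report the difference in effect with its 95% CI and p-value as the main output, and use 0.15 only as a descriptive flag. Keep the existing common-term test as a supplement.
- **Eye responders, both weeks, Definition 1 and likewise Definition 2:** compare the number of responding eyes per subject (0, 1 or 2) between best-eye-treated and worst-eye-treated subjects. Use a permutation test with a 95% CI on the risk-difference scale. Do not use an unadjusted comparison of paired GS010-versus-sham effects.
- **Interpretation:** state that a non-significant result is not evidence of no dependence.

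The cost is SAP wording, a few tables and a recorded reason for departing from the responder test in Protocol 12.4.2; no new data are needed. The drawback is wide intervals: half-widths of 0.40 to 1.21 LogMAR, and 0.36 to 0.48 for responders, under the assumptions above.

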### Responder Analysis

### Subject responders

The responder analyses at both Week 48 and Week 96 will be based on a randomization test comparing the observed rate of responders to the expected rate of responders under  $H_0$  (i.e. absence of treatment effect). Expected rate is defined as responder rate in the Sham group based on an improvement of at least 15 letters in the ETDRS score compared to baseline, or being greater than a Snellen acuity equivalent of 20/200.

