7.3.1 Visual Acuity

Enrolled subjects will include those able to read letters on the ETDRS chart (“on-chart” subjects) and those unable to read letters on the ETDRS chart but able to count fingers of the examiner at a given distance (“off-chart” subjects). On-chart subjects will have visual acuity measured with the ETDRS chart and an ETDRS score will be calculated. On-chart subjects will also have a Snellen acuity obtainable from the number of lines read on the ETDRS chart.

Off-chart subjects included in the study must maintain the visual ability to allow them to count fingers of the examiner as per the selection criteria. Off-chart subjects will not have an ETDRS score or a Snellen acuity obtainable from the ETDRS chart. Snellen acuity will be obtained utilizing the measured distance at which the subject was able to count the fingers of the examiner and a standardized formula available at ([Karanjia 2014](#)):

<http://www.countfingers.com/>

The Snellen acuities of on-chart and off-chart subjects will be converted to LogMAR for statistical analysis. Snellen acuities will be transformed to LogMAR using the standard formula available at:

<http://www.myvisiontest.com/logmar.php>

Additionally, 1 ETDRS line is considered equivalent to 0.1 LogMAR.

The visual testing at Visit 4 will be conducted for safety purposes and will not be analyzed as efficacy data (see [Section 7.6.3](#)).

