12.4.2 Secondary Analysis

The treatment estimate at Week 96 will be based on the same statistical approach as the primary endpoint analysis. Another analysis will compare time course of the response up to Week 96 using the mixed model procedure. The responder analyses at both Week 48 and Week 96 will be based on a McNemar test for paired samples. To verify whether the treatment effect is dependent upon the better-seeing eye or the worse-seeing eye at study entry, a test of homogeneity of subgroups (better-seeing or worse-seeing eye treated) effects in stratified paired binary data ([Zhao 2014](#)) will be performed.

Like the primary endpoint, a meta-analysis will be performed combining both studies (GS-LHON-CLIN-03A (RESCUE) and study GS-LHON-CLIN-03B (REVERSE)). A conditional logistic model will be used to assess the effect of better- and worse-seeing eye at study entry and the effect of time from onset of disease and the effect of treatment.

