## Responder

### Eye Responder

#### Definition 1

Responder at week 48 and also at week 96, will be defined by an improvement of at least 15 letters in the ETDRS score compared to baseline, *or* being greater than a Snellen acuity equivalent of 20/200. Early discontinuations (prior to W48 for the primary endpoint) will be considered as non responder. For week 96 two analyses will be performed: One for completers and one for subjects who don't have the Week 96 value available. If the week 96 ETDRS score is not available, then the previous visit value will be used.

#### Definition 2

Responder, at week 48 and also at week 96, will be defined by having an ETDRS Score equal to or greater than 20 letters. Early discontinuations (prior to W48 for the primary endpoint) will be considered as non responder. For week 96 two analyses will be performed: One for completers and one for subjects who don't have the Week 96 value available. If the week 96 visual acuity score is not available, then the previous visit value will be used.

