## Subject Responder

Responder, at week 48 and also at week 96, will be defined as a subject whose ETDRS score of the treated eye is at least 15 letters better than the sham eye *or* whose treated eye has a LogMAR acuity of at least 0.3 LogMAR better than the sham eye. Early discontinuations (prior to W48 for the primary endpoint) will be considered as non responder. For week 96 two analyses will be performed: One for completers and one for subjects who don't have the Week 96 value available. If the week 96 visual acuity score is not available, then the previous visit value will be used.

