#### Primary Analysis for EMA

The null and alternative hypotheses for the primary endpoint are defined below

$$H_0: \mu_{\text{All-GS010}} = \mu_{\text{All-Sham}}$$

$$H_1: \mu_{\text{All-GS010}} \neq \mu_{\text{All-Sham}}$$

Where  $\mu$  presents the mean change from baseline to Week 48 in LogMAR. “All” represents all eyes treated with GS010 or Sham

The primary analysis will be performed on the ITT population. The change from baseline to Week 48 in the LogMAR acuity will be the primary response. The change from baseline of all-GS010 eyes will be compared to the change from baseline of all-Sham eyes (intra-subject comparison) using a mixed model of analysis of covariance (ANCOVA) using the following terms (or covariate) in the model:

- Subject as random factor
- Eyes of the subject as random factor,
- Treatment and the
- Baseline LogMAR for each eye.

The analysis will be performed based on alpha of 0.05. The statistical significance in favor of GS010 against sham will provide evidence of the advantage of using GS010 for halting visual acuity loss or improving visual acuity in subjects with LHON with duration of vision loss of more than 6 months and up to 12 months. The difference in the mean change from baseline (adjusted mean difference) to Week 48 between the two treatment groups and associated 95% confidence interval will be reported.

The center will not be included in the analysis as the number of subjects recruited per site will be very small. However, stratification by geographical area will be performed as a sensitivity analysis. Neighboring countries can be pooled together to reach at least 9 subjects per geographical entity. The pooling will be performed during the masked review of data.

An additional model will add the treatment by geographical interaction for lack of generalizability of treatment effect purposes.

All the model diagnostics will be checked.

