### Eye responders

The responder analyses at both Week 48 and Week 96 will be based on a McNemar test comparing all-GS010 eyes against all-Sham eyes.

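### The subject-responder test in the SAP takes its expected rate under the null from a different event than its observed rate

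*SAP*

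**What the plan says.** SAP 5.4 (Subject Responder) counts as a responder "a subject whose ETDRS score of the treated eye is at least 15 letters better than the sham eye", or one "whose treated eye has a LogMAR acuity of at least 0.3 LogMAR better than the sham eye". Both limbs compare the two eyes at the visit; neither refers to baseline. Early discontinuations count as non-responders.

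SAP 9.5.5 (Subject responders) names a randomization test of the observed rate against the rate expected with no treatment effect, and then defines that rate: "Expected rate is defined as responder rate in the Sham group based on an improvement of at least 15 letters in the ETDRS score" relative to baseline, or acuity better than 20/200. This is Eye Responder Definition 1 of SAP 5.4, "an improvement of at least 15 letters in the ETDRS score compared to baseline" or better than 20/200, applied to the sham eye alone. The section gives no re-randomisation steps, sidedness or alpha.

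The protocol has no subject responder. Its section 12.4.2 says: "The responder analyses at both Week 48 and Week 96 will be based on a McNemar test for paired samples". The SAP keeps that at eye level as a "McNemar test comparing all-GS010 eyes against all-Sham eyes". SAP 9.5.3 spends the whole type I error on the primary endpoint and calls every other analysis supportive.

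**The concern.** A test of an observed rate against a null rate needs both to refer to the same event. Here they do not, and they respond to different things. If both eyes improve or decline together, the between-eye rate need not move, while the sham eye's own gain rate does. A sham eye better than 20/200 counts towards the expected rate even if its fellow sees equally well.

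The eyes that can qualify also differ. Protocol 7.3.1 states: "Off-chart subjects will not have an ETDRS score or a Snellen acuity obtainable from the ETDRS chart". An eye that stays off-chart therefore cannot meet the 15-letter limb of the expected rate, yet it can enter the observed rate through the 0.3 LogMAR limb.

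At stake is the p-value of one supportive responder analysis, planned at two time points. It could suggest benefit where there is none, hide a real benefit, or, if two-sided, suggest harm.

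**Working it through.** **Inputs from the documents.** 36 subjects; margin 0.3 LogMAR, set equal to 15 letters; SD 0.594 for the between-eye difference in change from baseline at Week 48 in the Phase I/II study (SAP 3.3).

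**Assumptions.** The SD for change is also used for the between-eye difference in level, which is what the responder event uses. The difference is normal with mean zero under no effect. The benefit tail is 2.5%.

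**The plan's own figure.** A paired t-test with d = 0.3/0.594 = 0.505, n = 36, two-sided 0.05, has power 83.8%. This reproduces the SAP's 84%. The SAP gives no power or error rate for the responder test.

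**Step 1: the true null rate of the between-eye event.** It is Φ(−0.3/SD).
- SD 0.594: Φ(−0.505) = 30.7%.
- A level SD would usually be larger, because the eyes already differ at baseline. With an assumed baseline between-eye SD of 0.40, independent of change, the level SD is √(0.40² + 0.594²) = 0.716, about 0.72, and the rate is Φ(−0.417) = 33.8%.
- Range: 22.7% at SD 0.4 and 35.4% at SD 0.8.

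**Step 2: sham rate used as a fixed null value.** Exact binomial, n = 36. The limit is the smallest count whose upper-tail probability under the sham rate is at most 2.5%. A true mean difference of 0.3 LogMAR makes the responder rate 50%.

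| Sham rate as null | Limit | False benefit, SD 0.594 | False benefit, SD 0.72 | Power at true 0.3 LogMAR |
|---|---|---|---|---|
| 20% | 13 | 29% | 45% | 97% |
| 25% | 15 | 11% | 20% | 88% |
| 30% | 17 | 2.7% | 7% | 69% |
| 40% | 21 | 0.05% | 0.2% | 20% |

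At a 20% sham rate, false benefit is 5% for SD 0.4 and 53% for SD 0.8. With the matched null of 30.7% (SD 0.594) it is 1.2%. A two-sided test at a 40% sham rate also rejects downwards at 8 or fewer responders: 18% false harm at SD 0.594.

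**Step 3: sham rate taken from the trial.** In practice the sham rate comes from the same 36 subjects. Simulation with no treatment effect, 20,000 trials per row; assumed baseline LogMAR mean 1.6, SD 0.4, between-eye correlation 0.5; SD of the between-eye difference in change held at 0.594; 15 letters taken as 0.3 LogMAR. In the last column the null comes from the between-eye event itself by flipping eye labels.

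| Mean change, both eyes (correlation of change) | Subject rate | Sham rate | False benefit at 2.5% | Two-sided error at 5% | Matched null, benefit tail |
|---|---|---|---|---|---|
| +0.2 (0.5) | 33.8% | 23.0% | 36% | 37% | 1.5% |
| 0 (0.5) | 33.9% | 34.0% | 10% | 19% | 1.7% |
| 0 (0.8) | 33.8% | 39.7% | 3.5% | 20% | 1.5% |
| −0.2 (0.5) | 33.8% | 46.7% | 1.0% | 36% | 1.5% |

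The subject rate stays near 34% while the sham rate moves with the common trend. Even where the two rates agree, false benefit is about 10%, because the sham rate is estimated and is negatively correlated with the observed event (about −0.26). It still exceeds 2.5% with the sham rate some 6 points above the subject rate. The simulation lets every eye qualify for the 15-letter limb; excluding eyes that stay off-chart would lower the sham rates shown.

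**The case against.** The SAP names a randomization test. Such a test generates its own reference distribution and needs no external null rate. If treatment labels were swapped in full and the difference between the subject rate and the sham rate recomputed each time, size would hold: 1.4 to 2.2% per tail in a null simulation with an assumed Efron coin of 2/3. On that reading no error is inflated. This part stands, and the error rates above apply only if the sham rate is used as the null value.

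It does not rescue the text. The SAP says the expected rate is defined as the sham rate. Either that sentence is followed and the null is wrong, or it is ignored and the plan does not describe the test that is run. Under the full swap, the statistic also subtracts the rates of two unlike events and has no clear meaning.

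It is also fair to object that the percentages rest on assumed inputs. They do: the 0.594 is given for change, and baseline and trend values are not in the documents. The figures are illustrations. The mismatch itself rests on the text alone.

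A reader might infer that the test is tilted towards GS010. The documents do not support that. They give no sham rate, and SAP 9.5.1 counts "halting visual acuity loss or improving visual acuity in subjects with LHON" as success, so sham-eye decline is not ruled out and neither is improvement. A reader might also look in the fixed-null table for a sham rate at which the test is right. None should be quoted, because such a value exists only if the sham rate is a known constant.

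**Conclusion.** Wrong as written, with minor reach. The stated expected rate is not the null rate of the event being tested, and nothing in the protocol or SAP links the two. Used as the null value, it can put the error well off nominal: in the illustration, false benefit runs from about 29% down to 0.1% as a fixed sham rate goes from 20 to 40% (45% down to 0.2% at a level SD of 0.72). Under a two-sided test, a high sham rate also produces false harm.

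It would go too far to infer that the trial's responder evidence or its main result is compromised. The subject responder appears only in the SAP, the eye-level McNemar test compares like with like, and neither the EMA nor the FDA primary analysis uses this rate.

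**What to change.** Delete the sentence that defines the expected rate. Keep the randomization test and write out its steps: re-randomise which eye was treated under the Efron allocation actually used, recompute the between-eye event each time, keep early discontinuations as non-responders throughout, and state the number of re-randomisations, the sidedness and the alpha.

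A simpler approximate alternative is a two-sided exact sign test of subjects whose treated eye is better by the margin against subjects whose sham eye is better by the same margin. It is exact only under independent fair-coin allocation, which Efron's method is not.

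The cost is a few lines of SAP text and one short program, with no new data and no change to the endpoint definition. Protocol Appendix V rules out SAP amendments once the randomization code is broken, so the change must come before the Week 48 unmasking.
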